7.2. Feasibility and recruitment modalities

The investigating centres have the following characteristics:

- The number of ablation of atrial fibrillation is greater than 50 per year,
- Transoesophageal echocardiography is performed routinely before any ablation of atrial fibrillation.

Investigating centres compliance with those characteristics will be documented upon selection.

In each centre, patient eligible for atrial fibrillation or left flutter ablation will be screened. In agreement with the physician performing the procedure, the study will be explained and proposed to the eligible patients by an investigator at the admission or at the pre-ablation consultation. It is strongly recommended to include patients consecutively in order to limit

selection bias. We plan to open circa 25 centres in France and Europe, with an average of 120 patients per centre. The provisional duration of enrolment is 30 months.

8. Material and Methods

8.1. Transoesophageal echocardiography

Transoesophageal echocardiography is performed according to the guidelines of the European Association of Cardiovascular Imaging (20).

It is performed at most within 48 hours before intervention.

Images must be stored locally for the duration of the study.

8.2. D-dimer assay

8.2.1. Material

STA - Liatest D-Di Plus will be used following the recommendations in its package insert on STAGO instruments. The STAGO instrument type used in each investigating centre will be documented (type and version) along with the name and lot of reagents (STA – Liatest D-Di Plus and its associated quality control plasmas).

8.2.2. Method

Blood sample (maximum 7.2 ml) will be collected for the determination of d-dimer level and for storage. It will be collected at the same time as standard biological intake and no more than 48 hours before surgery.

8.2.3. D-dimer assay

As STA-Liatest D-Di Plus assay reagents are pre-calibrated, the pre-calibration parameters will be used in each investigating centre. These will be entered on the analyzer through barcode scanning of the Assay Value insert, as described on the STA-Liatest D-Di Plus package insert.

As requested in by the Standard Operating Procedure, quality control (QC) samples will be run to ensure accuracy and reproducibility of the device each time a patient sample will have to be tested. Results of these QC have to fall within their acceptance ranges prior to testing any patient sample and will be collected along with patient's results.

8.3. ATE Score

Condition	Score
Hypertension	1
Heart failure	1
History of stroke	1
High plasma d-dimer level (> 270 ng/ml)	1

A zero ATE score is expected to exclude intra-atrial thrombi.

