BACKGROUND	Atrial fibrillation is the most frequent heart rhythm disorder. Its symptomatic forms, resistant to drug therapy, require invasive management (catheter ablation), which exposes to potentially serious complications including thromboembolic complications. Despite anticoagulant treatment, intra-atrial thrombus, which is a contraindication to catheter ablation, is detected in nearly 2 % of cases. Its diagnosis requires prior transoesophageal echocardiography, an unpleasant examination. The previous EXTRALUCID-d study showed that a zero ATE score, defined by no heart failure, no hypertension, no history of stroke, d-dimer < 270 ng/mL, has a negative predictive value of 100 % for the exclusion of intra-atrial thrombus.
PRIMARY OBJECTIVE	The objective of the study is to confirm the negative predictive value, sensitivity and specificity of the ATE score for the exclusion of intra-atrial thrombus.
SECONDARY OBJECTIVE(S)	
 • To determine the prevalence of atrial thrombi in the study population, • To determine the negative predictive value of the CHADS2VASC score of cardiac thrombus risk in the study population, • To determine the negative predictive value of the CHADS2 score of cardiac thrombus risk in the study population, • To collect a biobank of plasma samples to further confirm the study performances with other D-dimer assays.
OUTCOME(S)	The primary outcome is the number of patients with intra-atrial thrombus diagnosed by pre-procedural transoesophageal echocardiography.

STUDY TYPE	Prospective, multicentre diagnostic accuracy study in a standard of care setting.
MAIN INCLUSION CRITERIA	
 • Adult patients • Patients hospitalized for ablation of atrial fibrillation or symptomatic left atrial tachycardia • Affiliated person or beneficiary of a social security system • who have signed or orally given an informed consent
MAIN EXCLUSION CRITERIA	
 • Contraindication to transoesophageal echocardiography • Transoesophageal echocardiography made in another centre than the centre of ablation • Vulnerable persons • Refusal to participate in the study
INTERVENTION	
Patient management (preoperative assessment, intervention, surveillance, and follow-up) is carried out according to centre standard procedures.
 
An additional blood sample (7.2 ml) is collected for the d-dimer assay and the constitution of a biocollection.

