3.1.2. Description of the ATE score to be validated

A preliminary study, EXTRALUCID-d (NCT02199080), included 2,494 patients hospitalized for an atrial fibrillation ablation. It studied a combined clinical-biological score, the Atrial Thrombus Exclusion (ATE), associating thromboembolic risk factors (hypertension, cardiac insufficiency, history of stroke) and d-dimer level for the prediction of intra-atrial thrombus.

The primary outcome was the number of intra-atrial thrombus diagnosed by transoesophageal echocardiography. A zero ATE score, defined by no cardiac insufficiency, no hypertension, no history of stroke, and D-dimer < 270 ng/mL, had a negative predictive value of 100% for the diagnosis of intra-atrial thrombus.

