3.3. Overall risk/benefit assessment

We believe that the benefit / risk balance is very favourable, given that the risk of the study is negligible. The confirmation of an excellent negative predictive value of the ATE score would prevent one transoesophageal echocardiography out of three during the period of preoperative endocardial ablation of atrial fibrillation.

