8.4. CHADS₂ and CHA₂DS₂VASC scores

CHADS ₂ -> CHA ₂ DS ₂ VASC	
CHADS₂ Risk	Score
CHF	1
Hypertension	1
Age > 75	1
Diabetes	1
Stroke or TIA	2
From ESC AF Guidelines http://escardio.org/guidelines-surveys/esc-guidelines/GuidelinesDocuments/guidelines-afib-FT.pdf	
CHA2DS2-VASC Risk	Score
CHF or LVEF ≤ 40%	1
Hypertension	1
Age ≥ 75	2
Diabetes	1
Stroke/TIA/Thromboembolism	2
Vascular Disease	1
Age 65 - 74	1
Female	1

CHADS₂ and CHA₂DS₂VASC scores are stroke risk stratification schemes based on a risk factor approach (21–23).

9. Clinical data collection and procedure description

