11.1. Sample size rationale

Given the low rate of atrial thrombi (about 2 % of patients eligible to atrial fibrillation ablation), this study requires a high number of participants in order to allow reliable estimation of diagnostic performance.

To detect a 0.5 % deviation between two negative predictive values (binomial test), 2,000 patients are required for a power of 70 %; 2,400 patients for a power of 80 %; and 3,000 patients for a power of 90%.

Due to the high enrolment capacities of this multicentre study and its simplicity for the centres involved, it was chosen to focus on the power of the study and to retain a sample size of 3,000 patients.

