11.2. Statistical analysis plan

The analysis will be performed at the end of the trial. There is no interim analysis planned.

The index test is the ATE score. A zero score is a negative result, while a score above zero is a positive result.

The reference test is the transoesophageal echocardiography. The negative condition is the absence of thrombus, and the positive condition is the presence of thrombus.

Demographics, medical history, clinical characteristics and diagnosis will be presented in tables with descriptive statistics for each sub-population (positive and negative condition) and for the entire analysed population, as follows:

- For quantitative variables: mean and standard deviation,
- For qualitative variables: count, percentage (excluding missing denominator data) and 95% confidence intervals.

ATE score sensitivity, specificity, positive predictive value, negative predictive value, and 95% confidence intervals will be calculated.

Primary objective will be met, if these parameters are similar with the ones obtained during the first study.

The ATE score will be considered clinically relevant if a negative predictive value of 100 % is obtained for a zero score.

12. Ethical and legal aspects

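### The section 8.3 scoring table and the stated definition of a zero ATE score treat a D-dimer of exactly 270 ng/mL differently

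*Combined protocol and SAP*

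**What the plan says.** The D-dimer component of the ATE score appears in three places.

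- Synopsis, Background: the zero score of the earlier study is described with "no history of stroke, d-dimer < 270 ng/mL" among its conditions.
- Section 3.1.2, whose heading presents it as the description of the score to be validated: the same condition, "no history of stroke, and D-dimer < 270 ng/mL".
- Section 8.3, the only scoring table for this study: one point for "High plasma d-dimer level (> 270 ng/ml".

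Section 11.2 turns the score into a test result: "A zero score is a negative result, while a score above zero is a positive result". It gives no D-dimer cut-off of its own. It then sets the criterion for the primary objective: "Primary objective will be met, if these parameters are similar with the ones obtained during the first study". Separately, it calls the score clinically relevant only if the negative predictive value (NPV) at a zero score is 100%. The text available states no rounding rule for D-dimer and does not say explicitly how 270 is to be handled.

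**The concern.** A validation study should apply the same index test as the study it validates. Here the cut-off is written with a strict inequality on each side, and the boundary value falls to opposite sides depending on which section is followed. A patient at exactly 270 ng/mL with no hypertension, heart failure or stroke is test negative under section 8.3. Under the zero-score definition in the synopsis and section 3.1.2, the same patient is not.

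Two things depend on this. The accuracy estimates are to be compared with those of the first study, so a different rule adds a difference unrelated to how the score performs. The relevance criterion of a 100% NPV can also be lost on one patient, so no part of the cut-off should remain open to choice once results are known.

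**Working it through.** **Step 1. The two rules side by side**, for a patient with no clinical item:

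| D-dimer (ng/mL) | Section 8.3 (point if > 270) | Synopsis and 3.1.2 (zero if < 270) | Agree? |
|---|---|---|---|
| 269 | 0, negative | zero, negative | yes |
| 269.99 | 0, negative | zero, negative | yes |
| 270 | 0, negative | not zero, positive | **no** |
| 270.01 | 1, positive | not zero, positive | yes |
| 271 | 1, positive | not zero, positive | yes |

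The rules differ at one value only. A patient with any clinical item is positive under both, so only patients without one are affected.

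**Step 2. Inputs for the size of the effect**

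- Sample size 3,000 (section 11.1).
- Thrombus in "about 2 % of patients eligible to atrial fibrillation ablation" (section 11.1): 3,000 × 0.02 = 60 with thrombus and 3,000 − 60 = 2,940 without.
- Share of zero scores: section 3.3 says that confirming the score "would prevent one transoesophageal echocardiography out of three", so 3,000 / 3 = 1,000 zero scores and 2,000 positive.
- Assumption: all 60 thrombi are among the test positives.

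Base specificity is 1,000 / 2,940 = 34.0%. Its 95% half-width is 1.96 × √(0.340 × 0.660 / 2,940) = 1.71 points. Each thrombus-free patient at exactly 270 moves specificity by 100 / 2,940 = 0.034 points.

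**Step 3. How many patients.** The documents do not give this number. As an illustration, assume the 1,000 zero-score patients are spread evenly over the reportable values below 270 and that the value 270 is equally common.

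| | 1 ng/mL steps | 10 ng/mL steps |
|---|---|---|
| Patients at 270 | 1,000 / 270 = 3.7 | 1,000 / 27 = 37 |
| Shift in specificity | 3.7 / 2,940 = 0.13 points | 37 / 2,940 = 1.26 points |
| PPV, from 60 / 2,000 = 3.00% | 60 / 1,996 = 3.01% | 60 / 1,963 = 3.06% |
| Exact lower 95% limit of NPV with no false negative, from 0.025^(1/1,000) = 99.632% | 0.025^(1/1,004) = 99.633% | 0.025^(1/1,037) = 99.645% |

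The reporting step is neither stated nor excluded by the documents.

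**Step 4. The 100% NPV criterion.** The symbol decides this verdict only if there is a thrombus in a patient at exactly 270 with no clinical item and no other false negative in the trial. One such patient added to 1,000 thrombus-free zero scores gives an NPV of 1,000 / 1,001 = 99.9%, and the criterion fails. At the overall 2% prevalence, 3.7 patients would carry 3.7 × 0.02 = 0.07 expected thrombi, and 37 patients 37 × 0.02 = 0.74. The prevalence in patients with no clinical item may well differ from the overall figure.

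**The case against.** The strongest reply is that this study has only one operational rule. The synopsis and section 3.1.2 report the earlier study in the past tense, while section 8.3 sits in the methods and classifies every value. An analyst following section 11.2 would use that table and meet no gap. This is fair as far as it goes, but it does not remove the mismatch with the score named as the one to be validated.

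The wording may also be loose drafting rather than a different rule. The CHADS₂ table in section 8.4 scores age above 75, while section 5.2 defines a zero CHADS₂ score by age under 75, which leaves exactly 75 in the same position. This also bears on whether a symbol was lost when the document was converted to text. Section 8.4 preserves "CHF or LVEF ≤ 40" and a greater-or-equal sign, which suggests symbols survived, but the CHADS₂ age line could itself be a loss. That evidence is best treated as neutral.

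The case report form and the assay package insert are listed as appendices but are not in the text available. Either could settle the coding or the reporting step. The first study's rule is known only as these documents report it.

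Finally, the patient counts rest on assumptions. Section 11.2 gives no margin for similarity, so a shift of this size cannot be shown to change the judgement on the primary objective. Both points stand and limit the weight of the finding. They do not make the two definitions agree.

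**Conclusion.** The inconsistency is real and sits in the decision threshold of the index test. Confidence is high that the texts disagree at exactly 270. The size of any effect on the results is unknown and probably small: 0.13 points of specificity under the 1 ng/mL assumption and 1.26 points under the 10 ng/mL one, both below the sampling half-width of 1.71 points. PPV and the lower limit of NPV barely move. A change in the 100% NPV verdict is unlikely with fine reporting steps; with coarse steps it is less easily dismissed, since more patients would sit at the boundary. These figures rest on the even spread, the reporting step, the one-in-three share of zero scores, the 2% prevalence and all thrombi being test positive. The point is minor.

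**What to change.** Before analysis, reconcile the synopsis, section 3.1.2 and section 8.3 to a single inequality, the one actually applied in the first study. These documents report it as zero for values below 270; confirm this against the first study's own records. State the rule once in section 11.2, including how a reported value of exactly 270 is scored and whether results are rounded before the rule is applied. Check that the case report form and analysis code follow it.

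The cost is one symbol and one sentence. Conduct, data collection and sample size are unaffected.

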8.4. CHADS₂ and CHA₂DS₂VASC scores

CHADS ₂ -> CHA ₂ DS ₂ VASC	
CHADS₂ Risk	Score
CHF	1
Hypertension	1
Age > 75	1
Diabetes	1
Stroke or TIA	2
From ESC AF Guidelines http://escardio.org/guidelines-surveys/esc-guidelines/GuidelinesDocuments/guidelines-afib-FT.pdf	
CHA2DS2-VASC Risk	Score
CHF or LVEF ≤ 40%	1
Hypertension	1
Age ≥ 75	2
Diabetes	1
Stroke/TIA/Thromboembolism	2
Vascular Disease	1
Age 65 - 74	1
Female	1

CHADS₂ and CHA₂DS₂VASC scores are stroke risk stratification schemes based on a risk factor approach (21–23).

9. Clinical data collection and procedure description

9.1. Study calendar

Duration of inclusion: 30 months

Duration by subject: 48 hours at most (from enrolment to transoesophageal echocardiography result)

Total expected duration of the study: 30 months

9.2. Data collection requirements

	Screening (0 to 3 months)	Inclusion	Visit 1 (0 to 48 hours)
Inclusion/exclusion criteria	✓ (T)		
Informed consent		✓ (T)	
Medical history and demographics		✓ (S)	
Blood sample for D-dimer level assay		✓ (T)	
Transoesophageal echocardiography			✓ (S)

(T) Related to the clinical trial

(S) Standard care

Quality control samples results for D-dimer assay will also be documented.

9.3. Screening

Atrial fibrillation diagnosis may be based on a 12 lead electrocardiogram (ECG) characterized by absence of discrete P waves and an irregularly irregular ventricular rate. In most patients, a single ECG is sufficient to secure the diagnosis, assuming the patient is in AF at the time of the ECG. In some patients it may also be diagnosed using a heart rhythm recording such as a telemetry strip, Holter monitor, or an event monitor.

Women of childbearing age must have a negative beta-hCG blood test.

Patients with a programmed hospitalization for ablation of atrial fibrillation or symptomatic left atrial tachycardia are eligible to the study. The investigator verifies the eligibility criteria.

9.4. Enrolment

During the inclusion visit, the investigator informs the participant and answers all questions about the objectives, nature of constraints, foreseeable risks and expected benefits of the

research. He also specifies the rights of the participant and verifies the eligibility criteria. Oral consent of the patient will be recorded in the medical file.

Medical history, clinical data and demographics are collected (hypertension, diabetes, congestive heart failure, age, history of stroke, peripheral arterial disease and diagnosis).

Peripheral blood sample is collected for d-dimer assay.

9.5. Visit 1

The transoesophageal echocardiography is performed no more than 48 hours before ablation or during the ablation procedure. The vacuity of the left atrial appendage or the presence of a thrombus is specified on the transoesophageal echocardiography report. A spontaneous contrast and emptying velocity may be mentioned but these data are optional. Pictures of the left atrial appendage are recorded on CD if a thrombus is diagnosed.

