5.2. Secondary outcome

- Number of atrial thrombi in the study population
- Number of patients with atrial thrombus among patients with a zero CHADS2VASC score (no congestive heart failure, hypertension, diabetes mellitus, vascular disease [previous myocardial infarction, peripheral arterial disease or aortic plaque], history of stroke or transient ischemic attack, age under 75, and male)
- Number of patients with atrial thrombus among patients with a zero CHADS2 score (no congestive heart failure, hypertension, diabetes mellitus, history of stroke or transient ischemic attack, and age under 75)

6. Study design

This is a European multicentre prospective diagnostic accuracy study.

[figure not shown]

Figure 1 : Study design. TEE: transoesophageal echocardiography

7. Study population

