10.2.4. Information for data collection

All information required by the protocol must be recorded on the case report forms and an explanation must be provided for each missing data. The data must be collected as it is obtained and transcribed in these case report forms clearly and legibly.

Data will be collected through electronic case report forms.

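### The enrolment data list omits TIA, systemic thromboembolism, previous myocardial infarction and aortic plaque, so the CHADS2 and CHA2DS2VASC zero-score groups may be built on the wrong patients

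*Combined protocol and SAP*

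**What the plan says.** Section 9.4 (Enrolment) gives the only itemised list of history variables in the protocol: "hypertension, diabetes, congestive heart failure, age, history of stroke, peripheral arterial disease and diagnosis". The table in 9.2 has one general row for history and demographics.

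Three scores are to be computed from these data.

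- **ATE**, the index test. Section 8.3 gives one point for "History of stroke". Section 3.1.2 describes a zero score in the first study as "no cardiac insufficiency, no hypertension, no history of stroke, and D-dimer < 270 ng/mL". Neither place mentions TIA.
- **CHADS2**, a secondary comparator. Section 5.2 defines zero so as to require no "history of stroke or transient ischemic attack, and age under 75". Section 8.4 likewise gives two points for stroke or TIA.
- **CHA2DS2VASC**, a secondary comparator. Section 5.2 requires the absence of "vascular disease [previous myocardial infarction, peripheral arterial disease or aortic plaque], history of stroke or transient ischemic attack", among other conditions. Section 8.4 scores the cerebrovascular item as "Stroke/TIA/Thromboembolism" and vascular disease as a separate point.

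Section 10.2.4 adds a general rule: "All information required by the protocol must be recorded on the case report forms". The case report form is listed among the appendices in section 14, but its content is not in the supplied text.

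**The concern.** Section 4.2 makes the NPVs of CHADS2 and CHA2DS2VASC secondary objectives, and section 5.2 ties each to the thrombi found among patients scoring zero. A patient belongs in a zero group only if every component is known to be absent. If a component is never asked about, a patient who has it looks the same as one who does not, and is counted as zero.

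The 9.4 list leaves that gap for both comparators. A patient with a TIA and nothing else should score 2 on each, but would score 0. A patient with an old infarction and nothing else should score 1 on CHA2DS2VASC, but would score 0. The groups would be too large and would include patients whom the definitions exclude. Readers will set these NPVs beside that of ATE, so an error in them also distorts the comparison.

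**Working it through.** This is a comparison of texts. The plan states no figure on this point, so there is none to reproduce.

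**Step 1. Set each required component against the 9.4 list.**

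| Component | ATE (3.1.2, 8.3) | CHADS2 (5.2, 8.4) | CHA2DS2VASC (5.2, 8.4) | In the 9.4 list? |
|---|---|---|---|---|
| Hypertension | yes | yes | yes | yes |
| Heart failure | yes | yes | yes | yes |
| Diabetes | no | yes | yes | yes |
| Age | no | yes | yes | yes |
| Stroke | yes | yes | yes | yes |
| TIA | not mentioned | yes | yes | **no** |
| Systemic thromboembolism | no | no | yes (8.4 only) | **no** |
| Peripheral arterial disease | no | no | yes (named in 5.2) | yes |
| Previous myocardial infarction | no | no | yes (named in 5.2) | **no** |
| Aortic plaque | no | no | yes (named in 5.2) | **no** |
| Sex | no | no | yes | not named, but a demographic item |

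D-dimer, the fourth ATE item, comes from the blood sample. CHADS2 lacks one needed item and CHA2DS2VASC lacks four. ATE lacks none.

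**Step 2. Effect on a secondary NPV.** Let N patients truly score zero, with thrombus rate r, and let M patients be wrongly added, with thrombus rate s.

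- True NPV = 1 − r
- Recorded NPV = 1 − (N·r + M·s)/(N + M)
- Recorded minus true = −[M/(N + M)]·(s − r)

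The recorded NPV is too low if the added patients carry more thrombi than the true zeros, and slightly too high if they carry fewer. The direction is not known in advance.

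**Step 3. Scale only, not an estimate.** The documents give neither M nor N. Suppose, purely for arithmetic, a recorded zero group of 1,000 of whom 1%, 2% or 5% have TIA without stroke. Then M = 10, 20 or 50. With one thrombus among them and none elsewhere, the recorded NPV is 1 − 1/1,000 = 99.9% against a true 100%. For recorded groups of 500 or 1,500 it is 1 − 1/500 = 99.8% or 1 − 1/1,500 = 99.93%.

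**Step 4. ATE.** If sites record stroke alone under the stroke item, no patient changes ATE group. Patients move only if some sites also tick that item for TIA.

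**Step 5. Can 5.2 and 8.4 be applied together?** Not as written. For a zero CHA2DS2VASC score, 5.2 asks for "history of stroke or transient ischemic attack, age under 75, and male", while 8.4 gives a point for age 65 to 74. A man of 70 with no other factor is zero under 5.2 and scores 1 under 8.4. Complete data would not settle his group.

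**The case against.** The strongest reply is that the list in 9.4 is shorthand. It illustrates a general instruction to collect history, clinical data and demographics. It also omits sex, which CHA2DS2VASC needs, and nobody would conclude that sex goes unrecorded. Sections 5.2 and 8.4 make TIA and vascular disease necessary, and 10.2.4 requires everything the protocol needs to go on the form.

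Most of this stands as a limit on the claim. It rules out saying that patients will be misclassified; only that they may be. It does not remove the gap. The list includes diabetes and peripheral arterial disease, which are not ATE items, so it was evidently drawn up with the other scores in view. It is also the only list in the protocol text against which a site or a form designer could check.

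A reader might go further and infer that the primary result is at risk: a TIA-only patient with thrombus could be a false negative in one centre and a true positive in another, and section 11.2 calls ATE clinically relevant only at an NPV of 100%. The documents do not support this as a finding. The listed item and the ATE item use the same words, and nothing tells sites to enter TIA under stroke. What remains is that the term is undefined and about 25 centres will apply it.

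A reader might also put a number on it: 1% to 4% of 3,000 is 30 to 120 TIA-only patients; one third of these, 10 to 40, are otherwise zero; at 2% prevalence that gives 0.2 to 0.8 thrombi. This does not hold up. The TIA share has no source in the documents. The 2% is the whole-population rate, not that of patients otherwise at zero. The one third is the share of examinations that section 3.3 expects ATE to avoid, so the sum describes the ATE group, where the text shows no mismatch.

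**Conclusion.** The point holds for the two secondary comparators. The 9.4 list does not contain the data needed to score CHADS2 (TIA) or CHA2DS2VASC (TIA, systemic thromboembolism, previous myocardial infarction, aortic plaque) to their own definitions. If data are collected to that list, non-zero patients may enter both zero groups and the two NPVs would then describe the wrong patients. This depends on the case report form following 9.4, which cannot be checked.

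No size or direction is claimed, because the documents give no frequency for these histories and no thrombus rate among those who have them. No error in the ATE score or the primary rule is shown. Nor should 8.3 be read as excluding TIA: it does not say either way, and the answer lies in the first study's definition, which the documents do not give in that detail.

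**What to change.** 1. In 9.4 and the electronic case report form, record stroke, TIA, systemic thromboembolism, previous myocardial infarction and aortic plaque as separate items. Keep peripheral arterial disease.
2. Derive all three scores centrally from these items, not from a total entered by the site.
3. Score CHADS2 and CHA2DS2VASC on the components in 8.4, after reconciling the under-75 limit in 5.2 with the point for age 65 to 74 in 8.4.
4. State whether TIA counts as a history of stroke for ATE, using the first study's definition, since the aim is to validate that score. Add one sensitivity analysis under the other reading.

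The cost is four fields beyond the existing stroke item, taken from history that is already reviewed, and one extra table. The downside is slightly more data entry. If the form already holds the items, the first step reduces to correcting the list in 9.4.
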